[name].

E-mail: [contact]

Grant

1. The Health Ministry of China [grant number: 179]

- 2. Sun Yat-sen University Clinical Research 5010 Program [grant number: 2007048]
- 3. National Science Foundation of China [grant number: 81272635]
- 4. Science and technology fund for projects of Guangdong Province [grant number: 2012A030400007]
- 5. Zhejiang Provincial Science and Technology Major Projects [grant number: 2011C13039-2]

SCHEMA

Esophageal Cancer

Histology: squamous cell carcinoma

Staging: T1-4N1M0/T4N0M0 by the AJCC 6th edition

RANDOMIZATION

ARM 1 ARM 2

Neo-adjuvant Chemoradiotherapy

+ Surgery

Total Dose: 40.0 Gy

Dose / Fraction: 2.0Gy

Fraction / week: 5

Concomitant Vinorelbine $25 mg/m^2$ IV

Days 1, 8, 22 & 29

+ Cisplatin 75 mg/m² IV DRIP

Days 1 & 22

Or +Cisplatin 25mg/m² IV DRIP

Days 1, 2, 3, 4, 22, 23, 24 & 25

Surgery: same as ARM 2

McKeown esophagectomy or Ivor Lewis esophagectomy

Surgery

Follow-up at least every 3 months in the first year and every 6 months thereafter

1.0 BACKGROUND

Esophageal cancer (EC) is the eighth most common cancers in the world, with more than 480,000 new cases and 400,000 deaths occurred annually worldwide^[1]. In China, every year, no matter new cases or deaths account for more than half of the world. Besides, over 90% of Chinese EC patients have esophageal squamous cell carcinoma (ESCC).

Surgery is the main treatment of this disease, but the prognosis of patients with locally advanced esophageal cancer is rather poor. As a result of surgery alone, the 5-year survival rate of about 25% has not changed significantly in several decades^[2].

Preoperative chemoradiotherapy followed by surgery seems to hopefully improve the survival of EC. Nevertheless, the results of different studies were inconsistent^[2]. The CROSS trial has demonstrated that preoperative chemoradiotherapy can significantly increase the overall survival of patients with EC compared with surgery alone^[3]. It should be noticed that only 84 cases (23%) of ESCC were enrolled in this trial, which may be not perfect to evaluate the effect of this combined therapy for this tumor type. The FFCD9901 trial, which included 137cases (70.3%) of ESCC, has showed that there was no significant difference between the preoperative chemoradiotherapy and surgery alone group with respect to overall survival^[4].

Up till now, vinorelbine has no indications for esophageal cancer, although, some studied have reported its effect and feasibility to the therapy of EC^[5-7]. Vinorelbine has similar mechanism with paclitaxel and docetaxel, which are recommended for the chemotherapy of EC by NCCN. They are all classified as antimicrotubule agents, which cause mitotic arrest and eventual cell death through inhibition of microtubule dynamics. In comparison with the taxanes, vinorelbine has obvious advantage of little cardiac toxicity. This should be beneficial to prevent cardiac side effects of chemoradiotherapy, especially for the middle or lower thoracic EC, which account for over 70% of thoracic EC in China. For this group of patients, radiotherapy can hardly avoid cardiac toxicity.

Based on our preliminary study^[8], we have demonstrated the validity and safety of vinorelbine and cisplatin-based neoadjuvant chemoradiotherapy.

We are to carry out a phased III clinical trial to investigate the effect of this multidisciplinary therapy for the overall survival of patients with locally advanced ESCC.

2.0 OBJECTIVE

The purpose of this study is to compare neo-adjuvant chemoradiotherapy followed by surgery

versus surgery alone, in terms of the overall survival time (OS) in patients with Stage IIB or III squamous cell esophageal carcinoma.

3.0 STUDYDESIGN

The NEOCRTEC5010 trial is a multicenter, randomized phase III, clinical trial. The study started on 1 July 2007 and the duration of inclusion will be approximately 7 years. The study compares neoadjuvant chemoradiotherapy followed by surgery with surgery alone in patients with potentially curable locally advanced esophageal squamous cell carcinoma, with inclusion of 215 patients per arm.

4.0 ENDPOINTS

The primary endpoint is overall survival. The time from the date of randomization to the date of death or the last follow-up will be calculated as overall survival (OS).

As to secondary endpoints, we aim to compare disease-free survival (DFS), safety, rate of R0 resection, and pathologic response. The time from the date of R0 resection to the date of disease recurrence or death will be calculated as disease-free survival (DFS).

The toxicity of chemotherapy and radiotherapy will be evaluated according to the National Cancer Institute Common Terminology Criteria for Adverse Events Version 3.0 (CTCAE v 3.0). Perioperatively, the following will be evaluated: type of procedure, surgical resection rate, operation time, blood loss, thoracic drainage fluid volume, hospital stay, incidence of complications, and perioperative mortality.

5.0 STAGING CRITERIA – THE 6th AJCC EDITION

Primary Tumor (T)

TX	Davison	4		1_ ~	assessed.
1 X	Primary	HIIMOT	cannoi	ne	acceccen

- T0 No evidence of primary tumo
- Tis Carcinoma in situ
- T1 Tumor invades lamina propria or submucosa
- T2 Tumor invades muscularis propia
- T3 Tumor invades adventitia
- T4 Tumor invades adjacent structures

Regional Lymph Nodes (N)

NX Regional lymph nodes cannot be assessed

N0 No regional lymph node metastasisN1 Regional lymph node metastasis

Distant Metastasis (M)

MX Distant metastasis cannot be assessed

M0 No distant metastasisM1 Distant metastasis

Tumors of the lower thoracic esophagus:

M1a Metastasis in celiac lymph nodes

M1b Other distant metastasis

Tumors of the mid-thoracic esophagus:

M1a Not applicable

M1b Non-reginal lymph nodes and/or other distant metastasis

Tumors of the upper thoracic esophagus:

M1a Metastasis in cervical nodes

M1b Other distant metastasis

Stage grouping

Tis	N0	M0
T1	N0	M0
T2	N0	M0
T3	N0	M0
T1	N1	M0
T2	N1	M0
T3	N1	M0
T4	Any N	M0
Any T	Any N	M1
Any T	Any N	M1a
Any T	Any N	M1b
	T1 T2 T3 T1 T2 T3 T1 T2 T3 T4 Any T Any T	T1 N0 T2 N0 T3 N0 T1 N1 T2 N1 T2 N1 T3 N1 T4 Any N Any T Any N Any T Any N

6.0 PATIENT SELECTION

6.1 Inclusion Criteria

- a. Patients diagnosed with potentially resectable stage IIb or III thoracic esophageal squamous cell carcinoma (according to the 6th AJCC edition).
- b. With no previous treatment.
- c. With at least 6-month expected survival.
- d. Patients aged from 18 to 70.
- e. Adequate marrow: white blood cell $\geq 4.0 \times 10^9 / L$; neutrophil $\geq 1.5 \times 10^9 / L$; platelet $\geq 100.0 \times 10^9 / L$; hemoglobin ≥ 90 g/L.
- f. With normal liver and kidney function.
- g. Satisfactory performance status: Karnofsky performance score (KPS) \geq 90.
- h. Informed consent will be obtained before the study.

6.2 Exclusion Criteria

- a. Prior treatment to primary tumor or nodes.
- b. With allergic history or suspicious allergy to chemotherapy agents such as DDP and Vinorelbine.
- c. History of or concomitant hemorrhagic diseases.
- d. Surgery is not allowed because of other uncontrollable diseases.
- e. Pregnancy or lactation.
- f. Patients are incapable of signing informed consent due to psychological, family or social reasons.
- g. Reconstruction with stomach as the conduit are infeasible due to prior surgery.
- h. Patients have peripheral neuropathy and the CTCAE v3.0 grade is ≥ 2 .
- i. Prior malignancies except for adequately treated basal cell or squamous cell skin cancer, in situ cervical cancer.

6.3 Criteria for Removal from Protocol Treatment

- a. Distant metastasis is present during treatment.
- b. Intercurrent disease which would affect assessments of clinical status to a significant degree, require discontinuation of drug, or both.
- c. Unacceptable toxicity.
- d. Patients become intolerant of surgery after preoperative CRT.
- e. The patient may withdraw from the study at any time for any reason.

7.0 REGISTRATION GUIDELINES

- 7.1 All the patients must be registered with the coordinator of respective center prior to initiation of treatment
- 7.2 Registration form and consent form will be submitted.
- 7.3 The randomization desk will confirm all eligibility criteria and obtain essential information (including stratification factors and patient number).

8.0 STRATIFICATION / RANDOMIZATION SCHEME

8.1 Stratification

Patients will be stratified according to the treatment centers (SYSUCC vs. SUMCCH vs. TZH vs. SHCH vs. TJMUCH vs. FUSCC vs. ZJCH vs. SCH).

8.2 Randomization

Eligible patients will be randomized using a 1:1 allocation of patients to ARM1 and ARM2. Stratification factors for the randomization are centers defined in Section 8.1. The block sizes will be chosen by the statistician so that each block contains the patients in equal proportion. This procedure helps to ensure both randomness and investigator blinding (the block sizes are known only to the statistician), as recommended by Friedman et al^[9].Randomization will be generated by the statistician in sealed envelopes labeled by stratum. Only after the registration, the envelopes will be opened. Every patient will have a corresponding unique subject number during the whole study.

Eligible patients will be randomized to either:

ARM 1: Preoperative Chemoradiotherapy followed by Surgery or

ARM 2: Surgery alone.

9.0 EXAMINATIONS AND SCREENING OF PATIENTS

9.1 Examinations

All the patients should receive the following examinations before recruitment within 7 days before treatments.

9.1.1 Complete medical history and systemic physical examinations (including symptoms, signs, body weight loss and KPS).

9.1.2 Routine examinations:

- a. Routine blood tests (blood type, clotting time, hemoglobin, granulocyte count, platelet count, and granulocyte sorting).
- b. Serological examinations: liver and kidney function, blood lipids, blood glucose, blood electrolytes, and tumor markers.
- c. Electrocardiography.
- d. Lung function tests.
- e. Histopathology: pathological examination will be done based on the tissues from esophageal biopsy.
- f. X-ray: anterior-posterior and lateral chest X-ray, esophageal barium.
- g. Neck, chest and abdominal CT (plain and enhanced) from the first cervical spine to the umbilical plane.
- h. Esophagogastroduodenoscopy (EGD), with ultrasound endoscopy (EUS).
- i. Cervical ultrasonography.
- j. If necessary, electronic bronchoscopy will be employed to confirm the involvement of trachea and/or bronchus.
- k. If necessary, PET-CT will be employed to exclude distant metastasis.
- 1. If necessary, ECT will be employed to exclude bone metastasis.

9.2 Screening of patients

After examinations, patients are assessed according to the above-mentioned criteria, and those meeting the inclusion criteria and signing informed consent will be recruited into the study and will be randomized into the two treatment groups.

10.0 THERAPEUTIC PROTOCOLS

10.1 Protocol for patients receiving preoperative concurrent CRT and surgery (Figure 1)

10.1.1 Preoperative Chemotherapy

Patients will receive two cycles of vinorelbine and cisplatin. Vinorelbine, 25 mg/m², iv bolus, days 1 and 8. DDP, 75 mg/m², ivdrip, within 3hr,day 1 (or DDP, 25 mg/m², will be intravenously injected within 2hr, on days 1-4) every three weeks.

10.1.3 Preoperative radiotherapy

- 1) During CT simulation, patients will be immobilized with a vacuum bag in the supine position with arms raised. Radiation will be delivered by three-dimensional conformal radiotherapy (3DCRT) using 6-8 MV X-ray. The prescription dose to PTV should be 40 Gy in 20 fractions over 4 weeks, starting the first day of the first cycle of chemotherapy (*Figure 1*).
- 2) Gross tumor volume (GTV) is defined as the primary tumor and involved lymph nodes on CT and EUS. Clinical target volume (CTV) is defined as the GTV plus 3-cm proximal and distal margins and a radial margin of 0.5–1.0 cm, as well as elective nodal regions. Planning target volume is determined by adding 0.8 cm radially to the CTV.
- 3) The prescription dose will be specified at the International Commission on

Radiation Units and Measurements (ICRU) 50/62 reference point, which will usually be the isocenter. The isodose curve representing 93% of the prescription dose should encompass the entire PTV. Tissue density inhomogeneity correction will be performed. Radiation therapy will be delivered by the combination of anterior/posterior, oblique or lateral field. Customized blocks or a multi-leaf collimator will be used to shape the treatment fields. All patients will undergo a 3D planning. Beams-eye-view (BEV) displays will be used to ensure optimal target volume coverage and optimal normal tissue sparing.

4) Organs at risk (OARs) include both lungs, heart, spinal cord, and liver. Dose-Volume-Histograms (DVHs) will be used to select the most appropriate treatment plan and to evaluate the normal tissue damage. Standard dose constraints are applied for treatment plan: mean lung dose <17 Gy, total lung volume receiving greater than 20 Gy (V20) of <30%, heart V40 <30%, liver V30 <30%, and maximum spinal cord dose <45 Gy. Every effort should be made to keep the total lung dose to a minimum.

[figure not shown]

Figure 1 Time schedule of preoperative CRT

10.1.4 Criteria for radiation toxicity

- 1) The National Cancer Institute Common Terminology Criteria for Adverse Events v3.0 (CTCAE v3.0) is used for assessment of toxicity during radiotherapy.
- Acute and late toxicity related to radiation therapy include fatigue, myelosuppression, skin erythema, subcutaneous fibrosis, esophagitis, carditis, myelitis, and radiation pneumonitis.
- 3) In some cases, medical support and/or a feeding tube will be necessary. When grade 4 radiation-related toxicity is observed, active symptomatic treatment will be administered and radiotherapy will be withheld until the toxicity has recovered to Grade 3.
- 4) If any of the following toxicity is present, patients will be excluded from the treatment protocol: esophageal perforation and heavy hemorrhage, non-healing esophageal tracheal leakage, myocardial infarction, heart failure, severe arrhythmias, and radiation pneumonia with dyspnea.
- 5) If interruption of therapy (up to two weeks) becomes necessary, radiotherapy should be completed to the prescribed doses. Total number of fractions and

elapsed days should be carefully reported. If an interruption of more than two weeks is necessary, resumption of treatment is at the discretion of the radiation oncology chairs. The patient will be considered a major deviation, but follow-up will be continued.

10.1.5 Principles for the adjustment of dosage of chemotherapeutic agents

- 1) The CTCAE v3.0 guidelines will be used to evaluate toxicity from chemotherapy.
- 2) The dosage of chemotherapeutic agents will be adjusted according to the toxicity of the first course of chemotherapy (*Table 1*).

Table 1. Adjustment of chemotherapy dosage during the second course of chemotherapy

The most severe toxicity in the first course of chemotherapy (CTCAE v 3.0)	Vinorelbine	Cisplatin
Hematologic toxicity		
Granulocyte deficiency- related fever (body temperature ≥38.5 and grade 3/4 neutropenia regardless of duration)	75% of standard dose	75% of standard dose
Grade 4 thrombocytopenia or grade 3 thrombocytopenia with hemorrhage	75% of standard dose	75% of standard dose
Gastrointestinal reactions		
Grade 3 nausea/vomiting after prophylactic antiemetic treatment or symptomatic treatment	75% of standard dose or unchanged	75% of standard dose or unchanged

Grade 4 nausea/vomiting after prophylactic antiemetic	50% of standard dose	50% of standard dose
treatment or symptomatic		
treatment		
Other non-hematological tox	cicity	
Any grade 3 toxicity	75% of standard	75% of standard dose
	dose	
Any grade 4 toxicity	50% of standard	50% of standard dose or
	dose or	discontinuation of treatment
	discontinuation	
	of treatment	
Neurological toxicity		
Grade 2	50% of standard	50% of standard dose (no
	dose (no	delayed administration)
	delayed	
	administration)	
Grade 3 or 4	Treatment	Treatment suspended for up to 2
	suspended for	weeks; 50% of standard dose if
	up to 2 weeks;	improvement to grade 2
	50% of standard	toxicity, or treatment
	dose if	discontinued
	improvement to	
	grade 2 toxicity,	
	or treatment	
	discontinued	
Renal toxicity		
Creatinine clearance ≥ 60	Unchanged	Unchanged
ml/min		
50\(\leq\) Creatinine clearance <60	Unchanged	75% of standard dose
ml/min		
Creatinine clearance <50	Unchanged	Discontinue cisplatin.
ml/min		

10.1.6 Criteria for next course of chemotherapy:

- a. $ANC>1.5\times10^{9}/L$
- b. Platelet count $\geq 100 \times 10^9 / L$
- c. ALT, AST and total bilirubin ≤CTCAE v3.0 grade 2
- d. Non-hematologic toxicity (except for hair loss) returned to grade 1 or baseline level
- e. Neurological toxicity ≤CTCAE v3.0 grade 2

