10.1.7 Delayed chemotherapy

Chemotherapy will be delayed if, after a course of chemotherapy, the patient has failed to meet the criteria for the next course, and treatment will then be suspended for up to 2 weeks. Then, after 2 weeks, treatment will be halted if patients still do not meet the criteria for the next course of chemotherapy. Before the next course of chemotherapy, patients will undergo relevant laboratory examinations once a week and their recovery will be evaluated by the investigators. Chemotherapy will be reinstated if patients recover and meet the criteria for the next course of chemotherapy. The chemotherapeutic dosage will be adjusted if necessary.

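### For unresolved grade 2 neurological toxicity the protocol both gives and withholds the second chemotherapy course, and for grade 2 liver tests two restart criteria overlap without being reconciled

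*Protocol*

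**What the plan says.** Protocol section 10.1.6 lists five criteria, (a) to (e), for starting the next course. Three concern toxicity outside the blood counts:

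- Criterion (c) sets the limit for liver tests: "ALT, AST and total bilirubin ≤CTCAE v3.0 grade 2"
- Criterion (d) is worded as a general rule: "Non-hematologic toxicity (except for hair loss) returned to grade 1 or baseline level"
- Criterion (e) sets a separate limit for the nervous system: "Neurological toxicity ≤CTCAE v3.0 grade 2"

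Table 1 in section 10.1.5 sets the second-course dose by the worst toxicity in the first course. Its grade 2 neurological row gives both drugs at "50% of standard dose (no", and the bracket goes on to rule out delay. Its grade 3 or 4 neurological row suspends treatment for up to 2 weeks, then gives 50% on "improvement to grade 2" or else discontinues.

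Section 10.1.7 says what follows when a criterion is missed. A patient who has "failed to meet the criteria for the next course, and treatment will then be suspended for up to 2 weeks" is re-tested weekly, and "treatment will be halted if patients still do not meet the criteria for the next course of chemotherapy".

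**The concern.** Liver and neurological toxicities are non-haematologic, and (d) exempts neither. A patient due for course 2 with grade 2 neurological toxicity can therefore be treated at once under (e) and Table 1, or suspended and possibly halted under (d) and 10.1.7. Grade 2 liver tests pass (c) and fail (d).

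This is first a safety matter, because opposite instructions on a cytotoxic course apply to the same clinical state. It also matters for the data. Section 8.1 names eight centres, which may read the text differently. The chemotherapy delivered in ARM 1, the numbers delayed or halted, and the toxicity rates (safety is a secondary endpoint, section 4.0) would then partly reflect which line a centre followed.

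**Working it through.** **1. Apply each line to a patient who meets every other criterion.**

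| Status when course 2 is due | (c) or (e) | (d) | Table 1 |
|---|---|---|---|
| Neurological, grade 0–1 | met | met | no conflict |
| Neurological, grade 2 | (e) met | not met | 50% dose, no delay; also the resumption point after grade 3–4 |
| Neurological, grade 3–4 | (e) not met | not met | suspend |
| Liver tests, grade 0–1 | met | met | no conflict |
| Liver tests, grade 2 | (c) met | not met | no entry for grade 2 |
| Liver tests, grade 3–4 | (c) not met | not met | dose entries only |
| Other non-haematologic | no separate line | (d) alone decides | no competing restart threshold |

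The lines part company only at grade 2, and only for neurological toxicity and liver tests.

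**2. Does the baseline clause in (d) remove the conflict?** Largely not. Section 6.1 (f) requires normal liver function at entry, so grade 2 liver tests cannot be a baseline level. Section 6.2 (h) excludes peripheral neuropathy of grade 2 or higher, so that cannot be baseline either. Only a pre-existing grade 2 neurological condition of another kind could qualify.

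**3. Difference in timing.** The schema places course 2 on day 22. Radiotherapy is 20 fractions at 5 per week from day 1 (section 10.1.3). If day 1 opens a treatment week and nothing is interrupted, the last fraction falls on day 26. A full 2-week suspension moves course 2 to day 22 + 14 = 36, which is 10 days after radiotherapy ends, so the course is no longer concurrent. Surgery is timed from completion of chemoradiotherapy (section 10.1.9) and may move with it.

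**4. Difference in dose, only if grade 2 persists beyond the suspension.** Count planned chemotherapy as two equal courses at standard dose and read the halt as a halt of chemotherapy. The share at stake is (course 2 dose fraction) ÷ 2.

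- Neurological, worst grade 2, or grade 3–4 improved to 2: 0.50 ÷ 2 = 25%.
- Liver tests, worst grade 2, no reduction in Table 1: 1.00 ÷ 2 = 50%.
- Liver tests, worst grade 3 improved to 2, under the row for other non-haematologic toxicity: 0.75 ÷ 2 = 37.5%.

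If the patient recovers to grade 1 within 2 weeks, course 2 is given on either reading and only the delay differs.

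**5. How many patients?** The documents give no incidence. The 215 in ARM 1 is the arm size and so only a ceiling.

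**The case against.** The best defence is that (c) and (e) are specific rules and (d) covers whatever is left. Table 1 supports this in part: it lists neurological toxicity apart from its category of other non-haematologic toxicity, and both its neurological rows share the grade 2 threshold of (e). This may well be the intent. But (d) does not say so, and naming one exception suggests there are no others. For liver tests Table 1 gives less help, since they have no row of their own.

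A second defence is that all five criteria must be met together, so that (d) simply governs. For liver tests this works: (c) becomes redundant and nothing else collides with (d). For neurological toxicity it fails, because Table 1 still rules out delay at grade 2 and still permits resumption at grade 2.

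A third is that Table 1 grades the worst toxicity of course 1 while 10.1.6 grades status at restart. That could explain the grade 2 row if the toxicity has since resolved. It does not explain the grade 3 or 4 row, where improvement to grade 2 is itself a restart status.

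A reader might infer more than this supports: that the criteria conflict for non-haematologic toxicity in general, that half the chemotherapy is always at stake, that patients go straight from treatment to stopping, or that the primary result is compromised. The documents support none of these. The overlap is confined to two toxicities at one grade, Table 1 already halves course 2 for neurological toxicity, and 10.1.7 suspends before it halts. Overall survival is analysed by intention to treat whether or not treatment is completed (section 13.0), with randomisation stratified by centre (section 8.1).

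**Conclusion.** The inconsistency is real and narrow. For unresolved grade 2 neurological toxicity, (d) with 10.1.7 contradicts (e) and Table 1 on any literal reading. For grade 2 liver tests, (c) and (d) either conflict or (c) does no work.

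The readings differ by up to 2 weeks' delay and, only where grade 2 persists, by about a quarter of planned chemotherapy (neurological) or up to half (liver tests). These shares assume two equal courses and no other dose reduction. The number of patients affected cannot be estimated from the documents. Which threshold is appropriate is a clinical question on which no view is taken here. The sample size and error rates do not depend on it.

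**What to change.** Reconcile 10.1.6 (c), (d) and (e), the neurological rows of Table 1 and 10.1.7 so that each toxicity has one restart rule. Criterion (d) should state which toxicities it covers and which are governed elsewhere. The clinical team decides the thresholds. The cost is a protocol clarification and a notice to the centres, with no added procedures.

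The annual plan ends recruitment and treatment in December 2014. If treatment is already complete, record instead which rule each centre applied, and classify second-course delays and halts on one common definition when reporting delivery and toxicity in ARM 1. That costs a query to each centre and a review of the affected ARM 1 records.
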